### 13.1 Immunogenicity Analysis

The primary immunogenicity analysis will compare the anti-chikungunya PRNT50 antibody geometric mean titer (GMT) 28 days after one or two immunizations in the Per Protocol (PP) analysis population between the treatment groups. GMTs and GMT ratios will be estimated by applying an analysis of variance including the factor vaccination group. This will be done using log-10 transformed data and taking the anti-log of the resulting point estimates for the least squares means, least squares means differences and the corresponding 2-sided 95% CIs. P-values will also be provided to compare GMTs for the MV-CHIK groups (pairwise comparisons adjusted for multiple comparisons according to Tukey-Kramer; groups A vs. B, C vs. D, M1 vs. M2), e.g. 28 days after the 2nd MV-CHIK dose, etc. Likewise, SCRs will also be compared between groups. Seroconversion will be defined as anti-Chikungunya PRNT50 titers  $\geq 10$ .

Measles ELISA titers will be analyzed as described above. In addition, the effect of pre-existing anti-measles immunity will be assessed: The CHIKV PRNT50 titers 28 days after first vaccination, between the four baseline measles titer groups, defined by baseline percentiles

(25%, 25-50%, 50-75%, 75-100%), will be compared. No stratification by dose groups is intended.

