### **13.5.3 Per-Protocol (PP) Population**

As a primary analysis, immunogenicity will be assessed on the per-protocol (PP) population. The PP population includes subjects who have received at least one vaccination. Subjects with protocol deviations that could have an impact on immune response will be excluded from the PP Population. Examples that may lead to exclusion from the PP population are provided here (further criteria may be defined in the SAP):

- Immunosuppressive drugs: Use of corticosteroids (excluding topical preparations) or immunosuppressive drugs within 30 days prior to vaccination, or anticipated use during the trial.
- Subjects with any confirmed immunosuppressive or immunodeficient condition, including human immunodeficiency virus (HIV), hepatitis A, B or C infection or a family history of congenital or hereditary immunodeficiency
- Subjects who received the wrong or no study medication

These criteria for potential protocol violation have been identified at the time of planning the study. However, during the course of the trial unforeseen events may occur or new scientific knowledge may become available, therefore final decisions on whether any protocol violation could impact immune response and thus lead to exclusion from the PP population will be made by the sponsor on a case by case basis in a blinded manner (and prior to study unblinding). Sample testing issues may also lead to exclusion from the PP population for particular time points.

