2.2 Conduct of Analysis

2.2.1 Preliminary Analysis

A preliminary analysis including safety and immunogenicity data will be performed in August 2017. The analysis was initially planned to be conducted after all subjects completed Visit 3 (Day 56) but was re-scheduled due to unforeseen delays to enable further vaccine development progress. The goal of this analysis is to provide highly valuable data of the novel Chikungunya vaccine for further development. Results from this analysis will have no impact on the study design and treatment of the subjects in this study.

All tables and listings marked with an "x" in column "IA" in section 10.1 and 10.1 will be generated for this Preliminary Analysis.

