2.14 Protocol Deviations

Protocol deviations will be collected only for the final analysis from the study database. The listing of protocol deviations will be prepared by Assign Data Management and Biostatistics GmbH using information from the eCRF documentation as well as from monitoring.

Protocol deviations will be identified during a Blind Data Review Meeting (BDRM) attended by Assign Data Management and Biostatistics GmbH and Themis Bioscience GmbH (sponsor).

SAP (MV-CHIK-202, FINAL 3.0, 09-May-2018) Page 19 of 47 Based on: STAT03_A Statistical Analysis Plan Version 5.0, Effective Date 16-Dec-2016 Confidential and intellectual property of Assign DMB. No part of this document or its contents may be duplicated, referenced, published or otherwise disclosed in any form or by any means without prior written consent of Assign DMB.

The BDRM will take place after all outstanding queries have been resolved. Protocol deviations will be classified into major or minor protocol deviations based on their possible impact to the study results. Protocol deviations are defined as "major" if they are likely to affect the outcome of the study (e.g. effect on target variables). During the course of the study unforeseen events may occur or new scientific knowledge may become available, therefore final decisions on all protocol deviations for this analysis will be made on a case by case decision in the BDRM.

Subjects with major protocol deviations will be part of the Safety Population and mITT Population, but not part of the Per-Protocol Population (PP Population). Minor protocol violations will be regarded as fully evaluable and, therefore, will be part of the PP Population.

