2.16 Analysis Populations

Three analysis populations will be used in this analysis:

• Modified Intent-to-Treat (mITT) Population

The exploratory immunogenicity analyses will be based on the modified ITT population. The modified Intent-to-treat (mITT) analysis population is defined to include all subjects randomized who receive at least one vaccination. Subjects will be analyzed according to the treatment group to which they are randomized to, rather than by the actual treatment they received.

• Safety Population (Final Analysis only)

All safety analyses will be based on the Safety population, which is defined to include all subjects who entered into the study and receive at least one vaccination. All analysis based on the Safety population will be carried out using the actual treatment received.

• Per-Protocol (PP) Population (Final Analysis only)

The Per-Protocol population is defined as mITT population excluding those subjects with at least one major protocol deviation. The PP population will exclude an enrolled subject if one of the following criteria is met:

- Immunosuppressive drugs: Use of corticosteroids (excluding topical preparations) or immunosuppressive drugs within 30 days prior to vaccination, or anticipated use during the trial.
- Subjects with any confirmed immunosuppressive or immunodeficient condition, including human immunodeficiency virus (HIV), hepatitis A, B or C infection or a family history of congenital or hereditary immunodeficiency
- Subjects who received the wrong or no study medication
- Subjects with other major protocol deviations

SAP (MV-CHIK-202, FINAL 3.0, 09-May-2018) Based on: STAT03_A Statistical Analysis Plan Version 5.0, Effective Date 16-Dec-2016 Confidential and intellectual property of Assign DMB. No part of this document of Page 20 of 47

These criteria for potential protocol violation were identified at the time of planning the study. However, during the course of the trial unforeseen events may occur or new scientific knowledge may become available, therefore final decisions on whether any protocol violation could impact immune response and thus lead to exclusion from the PP population will be made by the sponsor on a case by case basis in a data review meeting. Sample testing issues may also lead to exclusion from the PP population for particular time points.

Changes in the Conduct of the Study or Planned Analysis 2.17

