The statistical analysis plan is based on the final study protocols for Austria (Version 1.5; 24-Nov-2016) and Germany (Version 1.6; 19-Apr-2017). No changes in the conduct of the planned analysis as described in the CSP are intended.

However, the time point of the Preliminary Analysis was moved forward to August 2017. The Preliminary Analysis was initially planned to take place after all subjects completed Visit 3.

Page 21 of 47

3. **OVERALL STUDY INFORMATION**

Treatment groups for the preliminary analysis as well the final analysis are defined in section 2.3. Overall study information analysis will be prepared for the:

- Preliminary analysis: mITT population. •
- Final analysis: Safety, mITT and PP population. •

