6.1 Primary Endpoint

The primary immunogenicity endpoint is the immunogenicity on Day 56 in the mITT population confirmed by the presence of functional antibodies as determined by the plaque reduction neutralization test (PRNT₅₀).

Following tables will be provided:

SAP (MV-CHIK-202, FINAL 3.0, 09-May-2018) Based on: STAT03_A Statistical Analysis Plan Version 5.0, Effective Date 16-Dec-2016 Confidential and intellectual property of Assign DMB. Page 26 of 47

Confidential and intellectual property of Assign DMB. No part of this document or its contents may be duplicated, referenced, published or otherwise disclosed in any form or by any means without prior written consent of Assign DMB.

- Number of functional antibodies blood samples drawn (yes/no) will be tabulated by treatment group and overall (frequency statistics).
- The geometric mean titer (GMT) of the functional antibodies by PRNT₅₀ will be tabulated by treatment group and overall (summary statistics).

Statistical analysis will be performed as described in section 2.7.1.

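### Protocol and SAP name different primary populations (PP versus mITT) with no declared change, and no firewall is described between the preliminary by-treatment listings and the sponsor's later PP exclusions

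*SAP*

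**What the plan says.** **Primary population.** Protocol 13.5.3 states: "As a primary analysis, immunogenicity will be assessed on the per-protocol (PP) population". Protocol 13.1 (and the synopsis) places the primary GMT comparison "28 days after one or two immunizations in the Per Protocol (PP) analysis population between the treatment groups". Protocol 13.5.2 reserves mITT for exploratory work. SAP 6.1 states instead: "The primary immunogenicity endpoint is the immunogenicity on Day 56 in the mITT population confirmed by the presence of functional antibodies". In SAP 10.1 the two results tables labelled as the primary endpoint (3.1.2 and 3.1.3) are mITT, and PP appears only as repeat tables 3.2.1 to 3.2.26. SAP 2.16 keeps the protocol's description of mITT as exploratory. SAP 2.7 limits inference to PP and an ITT population that is not among the three defined in 2.16. SAP 2.17 says: "No changes in the conduct of the planned analysis as described in the CSP are intended". The only departure it records is the earlier date of the preliminary analysis.

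**Who settles PP, and when.** Protocol 13.5.3 says the final decisions "will be made by the sponsor on a case by case basis in a blinded manner (and prior to study unblinding"). SAP 2.16 repeats the sentence with a different ending: they "will be made by the sponsor on a case by case basis in a data review meeting". SAP 2.14 adds: "Protocol deviations will be collected only for the final analysis from the study database". It calls the meeting a Blind Data Review Meeting, attended by the data-management contractor and the sponsor. SAP 2.16 marks PP as existing for the final analysis only.

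**Preliminary analysis.** SAP 2.2.1 says: "A preliminary analysis including safety and immunogenicity data will be performed in August 2017". It generates every output marked in the IA column. These include Table 3.1.3 (the primary ANOVA by treatment group) and Listing 3.1, whose columns include subject number, treatment group and PRNT titre.

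**The concern.** The primary population decides which number is the trial's headline result. If two governing documents disagree, and one of them also disagrees with itself, two analysts can report different GMT ratios and each cite a valid source. Because the change is not declared, a reader of the final report cannot tell whether it was made for a stated reason or when.

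The second matter is the order of events. Case-by-case exclusion is acceptable when those deciding cannot know the outcome. Here the Day 56 titres are tabulated and listed by treatment before PP membership is fixed. The protocol's explicit condition on blinding is missing from the SAP paragraph that governs PP.

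Third, PP is defined once for the whole trial rather than by visit. An event months after the Day 56 sample could therefore remove a titre that it cannot have affected.

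**Working it through.** **1. Primary population, side by side**

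| Source | PP | mITT |
|---|---|---|
| Protocol synopsis, 13.1, 13.5.3 | primary | – |
| Protocol 13.5.2 | – | exploratory |
| SAP 6.1; Tables 3.1.2, 3.1.3 | repeat tables 3.2.x | primary |
| SAP 2.16 | not ranked | exploratory |
| SAP 2.7 | named, not ranked | undefined ITT named instead |
| SAP 2.17 | no change of population declared | no change of population declared |

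All of this is current text. The protocol is consistent with itself. The SAP contradicts both the protocol (6.1 against 13.5.3) and itself (6.1 against 2.16).

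**2. Sequence**

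- Preliminary analysis: planned for August 2017, mITT only (SAP 2.2.1 and section 6). It includes Listing 3.1 and Table 3.1.3.
- Final analysis: deviations are collected and PP is formed (SAP 2.14, 2.16), with the sponsor deciding case by case.

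The documents do not use the word unblinded for the preliminary analysis. A listing that shows treatment group and an ANOVA by treatment group nevertheless require someone to hold the allocation. Neither document says who receives these outputs or bars the PP deciders from them. SAP 2.2.1 says the results will not affect study design or the subjects' treatment, but that assurance does not extend to analysis populations.

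**3. Events after Day 56**

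SAP 2.16 removes a subject from PP for any one major deviation. Only sample-testing problems are tied to particular time points. For the corticosteroid criterion, with its limit of 30 days before a vaccination:

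- Groups A–D, use on Day 180: 196 − 180 = 16 days before the last injection, so the limit is met and the Day 56 titre is removed as well.
- Groups A–D, use on Day 150: 196 − 150 = 46 days (186 − 150 = 36 at the early edge of the ±10-day window), so the limit is not met.
- Groups M1/M2, use on Day 150: 168 − 150 = 18 days, so the limit is met.

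Loss of a valid Day 56 titre is therefore possible under the text, but it does not follow from every late event.

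**4. The plan's own figures (protocol 13.4)**

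- Dose against dose, 60 per group: log10(45.7/22.4) = 0.310; standard error 0.6 × √(2/60) = 0.1095; ratio 2.83 on 118 df gives 80.1% power (stated 80%).
- Vaccine against control, 60 and 10: log10(15.4/7.3) = 0.324; standard error √(0.36/60 + 0.0676/10) = 0.1130; ratio 2.87 with Satterthwaite df gives 79.2% (stated 80%).

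Both figures reproduce. They assume that all 60 and 10 subjects are analysed, so a PP primary carries no allowance for exclusions. No exclusion rate is given. Assuming random exclusion of 5, 10, 15 or 20% (57, 54, 51 or 48 per group), dose-against-dose power becomes 78.0, 75.7, 73.3 or 70.6%.

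**5. Sensitivity of the result to selective exclusions (illustration)**

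Inputs: a group of 60 with GMT 45.7 (the Phase 1 high-dose Day 28 value in protocol 13.4), three subjects below 10 removed, each carried as 5 under the SAP section 6 substitution rule.

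(60 × log10 45.7 − 3 × log10 5)/57 = (99.595 − 2.097)/57 = 1.7105, and 10^1.7105 = 51.3. The ratio is 51.3/45.7 = 1.12.

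A simulation took two groups of 60 with no true difference, log10 SD 0.6, an unadjusted two-sided 5% t-test and 20,000 runs, and dropped the lowest titres from one group:

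| Dropped | GMT ratio | Rejection |
|---|---|---|
| 0 | 1.00 | 4.9% |
| 1 | 1.05 | 5.8% |
| 2 | 1.10 | 7.4% |
| 3 | 1.15 | 9.6% |
| 6 | 1.30 | 19.9% |

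This is a worst-case pattern. The SAP's Tukey-Kramer adjustment would change the rejection rates.

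**The case against.** **The meeting is called blind.** SAP 2.14 names it so, and SAP 2.17 says the protocol's analysis is unchanged. That is a real safeguard on paper and it stands. What remains is that the blinding wording is inconsistent within the SAP, and that a name does not keep the meeting blind if attendees could already hold the listings.

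**A reader might infer that the sponsor's deciders saw the titres by treatment.** The documents do not say so. The stated purpose of the preliminary analysis, to inform further vaccine development, makes sponsor access plausible but does not establish it.

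**A reader might infer that mITT was made primary after the results were known,** because SAP 3.0 is dated 09-May-2018, about nine months after August 2017. Earlier versions are not available, and the text still describes the preliminary analysis as a future event. When mITT became primary is unknown.

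**A reader might infer that any late event removes a Day 56 titre.** It does not. The Day 150 example above meets the 30-day limit only in M1/M2. A subject who misses only the Day 196 injection does not clearly fall under the criterion for having received incorrect or no medication.

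**The two halves offset each other.** If mITT is the headline, PP exclusions cannot move it. This is correct: the exclusion risk bears on the primary result only if PP is primary, as the protocol has it.

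**The magnitude is hypothetical.** This stands too. The GMT is a Phase 1 Day 28 value, the exclusions are assumed, and 12% is small beside the roughly two-fold difference (45.7 against 22.4) in the sample size justification.

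**Conclusion.** The contradiction on the primary population is established from the text alone and needs no assumption. It should be resolved before the final analysis is reported, because each of two results could be presented as primary under a governing document.

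The gap in safeguards is also established, but as a gap: by-treatment titres are listed before PP is settled, the protocol's blinding condition is absent from SAP 2.16, and no firewall is described. The documents do not support saying that decisions were made with knowledge of the results.

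That PP is not visit-specific is likewise clear. How many Day 56 titres this would cost is unknown. The +12% and the simulated rejection rates show only how sensitive a PP result could be to a few selective exclusions. They are not estimates for this trial.

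**What to change.** 1. **One primary population throughout the SAP.** mITT as in SAP 6.1 is preferable because it needs no case-by-case exclusions. Remove the exploratory label in SAP 2.16. Log the choice in SAP 2.17 as a departure from protocol 13.1 and 13.5.3, and state when it was made relative to the preliminary analysis, since adopting it afterwards would itself be a change made after data were seen. Report PP alongside. If PP is kept as primary, correct SAP 6.1 and the labels of Tables 3.1.2 and 3.1.3.
2. **SAP 2.7:** replace ITT with mITT.
3. **SAP 2.16:** restore the protocol's blinding wording. Have PP membership decided by people without access to the preliminary outputs, from listings without titre or treatment group. Record who had access to those outputs.
4. **Visit-specific PP:** for the Day 56 analysis, count only deviations up to the Day 56 sample.

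**Cost.** A SAP revision, a declared change to the planned analysis and an access restriction. No new data are needed, and tables for both populations are already planned. If the protocol text is changed as well, protocol 17.1 requires ethics committee approval, and the SAP rests on two national protocols.

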6.2 Functional Antibodies Assessment

6.2.1 Preliminary Analysis

For the Preliminary Analysis immunogenicity blood samples are taken at Visit 1 (Day 0), Visit 2 (Day 28), Visit 3 (Day 56), ET visit (if ET up to Day 56) and for M1 and M2 additionally at Visit 0 (Day -28).

Following tables will be provided:

- Number of functional antibodies blood samples drawn (yes/no) will be tabulated by visit, treatment group and overall (frequency statistics).
- The geometric mean titer (GMT) of the functional antibodies by PRNT₅₀ will be tabulated by visit treatment group and overall (summary statistics).
- The seroconversion rate PRNT_SC by visit, treatment group and overall (frequency statistics).
- The geometric mean titer (GMT) of the functional antibodies by ELISA will be tabulated by visit treatment group and overall (summary statistics).

Following listing will be provided:

- A data listing of functional antibodies PRNT details will be provided (incl. visits).
- A data listing of functional antibodies ELISA details will be provided (incl. visits).

Statistical analysis will be performed as described in section 2.7.2.

6.2.2 Final Analysis

Immunogenicity blood samples for the final analysis are statistically analyzed for Visit 1 (Day 0), Visit 2 (Day 28), Visit 3 (Day 56), Visit 5 (Day 196), Visit 6 (Day 224) and ET visit. Additionally for treatment groups M1 and M2 samples are taken at Visit 0 (Day -28), Visit 4 (Day 168).

Following tables will be provided:

- Number of functional antibodies blood samples drawn (yes/no) will be tabulated by visit, treatment group and overall (frequency statistics).
- The geometric mean titer (GMT) of the functional antibodies by PRNT₅₀ will be tabulated by visit treatment group and overall (summary statistics).
- The geometric mean titer (GMT) of the functional antibodies by ELISA will be tabulated by visit treatment group and overall (summary statistics).
- The seroconversion rate PRNT_SC by visit, treatment group and overall (frequency statistics).
- The seroconversion rate ELISA_SC by visit, treatment group and overall (frequency statistics)

Following listings will be provided:

- A data listing of functional antibodies PRNT details will be provided by visits.
- A data listing of functional antibodies ELISA details will be provided by visits.

Statistical analysis will be performed as described in section 2.7.2

6.4 Measles Antibodies Assessment

Measles antibody titers are taken at, at Visit 1 (Day 0), Visit 2 (Day 28), Visit 3 (Day 56), and for M1 and M2 additionally at Visit 0 (Day -28) and ET visit if applicable.

Following tables/listing will be provided for the Preliminary and Final Analysis:

- The number of measles antibody titer samples drawn (yes/no) will be tabulated by visit, treatment group and overall (frequency statistics).
- The geometric mean titer (GMT) for the variable measles antibodies by ELISA will be tabulated by visit, treatment group and overall (summary statistics).
- A data listing of measles antibody results will be provided by visits.

6.5 T-cell Analysis

6.5.1 Preliminary Analysis

Samples of a subset of subjects (only in Vienna) will be analyzed for T cell immune response. Chikungunya virus specific T cells will be analyzed on Visit 3 (Day 56).

Following tables/listing will be provided:

- The number of functional Chikungunya virus specific T cells at Visit 3 by treatment group and overall (summary statistics).
- The geometric mean value for T cell immune response by treatment group and overall (summary statistics).
- A data listing of T-cell details will be provided.

Statistical analysis for T-cells will be performed as described in section 2.7.2

6.5.2 Final Analysis

Samples of a subset of subjects (only in Vienna) will be analyzed for T cell immune response at Visit 1 (Day 0), Visit 2 (Day 28), Visit 3 (Day 56), Visit 5 (Day 196) and Visit 6 (Day 224) and additionally on Visit 4 (Day 168) for treatment group M1 and M2 and ET visit if applicable.

Following tables/listing will be provided:

- The number of functional, Chikungunya virus specific T cells by visit, treatment group and overall (summary statistics).
- The geometric mean value for T cell immune response tabulated by visit, treatment group and overall (summary statistics).
- A data listing of T-cell details will be provided by visits.

Statistical analysis for T-cells will be performed as described in section 2.7.2

